9.2.2.3. Index Date

The index date for the COVID-19 Source and the Trial Similar Subcohort will be defined as the date of first date tested positive or diagnosed for COVID-19 (ie, positive PCR or antigen results of direct SARS-CoV-2 viral testing or have confirmed COVID-19 diagnosis codes) during the study period.

Method to refine index date per research question will be defined in SAP.

The index date for the Paxlovid cohort will be defined as the date of first prescription of Paxlovid during the study period.

9.2.2.4. Follow-up

The follow-up period starts at index date and participants will be followed until the date of the first occurring of the following events:

- Death;
- At the end of their database disenrollment from the database;
- At the end of study period (Section 9.2.2.1);
- Occurrence of the outcome of interest.

Follow-up time for hospitalized patients will meet the criterion in Section 9.2.1 (ie, hospitalized within 30 days of COVID 19 diagnosis or index date). Details as well as follow-up windows for long COVID will be defined in SAP.

9.3. Inclusion and Exclusion Criteria

The inclusion and exclusion criteria for the source cohort, trial similar cohorts (TSC), and Paxlovid cohort are described respectively in this section. Figure 3 shows the inclusion and exclusion assessment windows.

[figure not shown]

Figure 3. Inclusion & Exclusion Assessment Windows (Days)

9.3.1. Inclusion Criteria

9.3.1.1. COVID- 19 Source Cohort, TSC Standard Risk Cohort and TSC High Risk Cohort

Patients in the COVID-19 Source cohort, TSC – standard risk (C4671002) or high risk cohort (C4671005), must meet all of the following inclusion criteria to be eligible for inclusion in the study:

- Tested positive or diagnosed for COVID-19 (i.e. positive PCR or antigen results of direct SARS-CoV-2 viral testing or have confirmed COVID-19 diagnosis codes: SARS-CoV-2L severe acute respiratory syndrome coronavirus 2; PCR: polymerase chain reaction) during the study period.
- At least 12 months of ≥1 healthcare activity prior to index date (Section 9.2.2.3)
- Integrated delivery network information to allow linkage of outpatient and inpatient records

In addition to inclusion criteria above, patients in the high risk cohort (C4671005) must meet the following inclusion criteria:

- Has at least 1 characteristic or underlying medical condition associated with an increased risk of developing severe illness from COVID-19 at baseline (unless specified otherwise) including:
 - a. \geq 60 years of age at the index date;

- b. Body mass index (BMI) >25 kg/m²;
- c. Current smoker (cigarettes smoking at baseline).
- d. Immunosuppressive disease (eg, bone marrow or organ transplantation or primary immune deficiencies) OR prolonged use of immune-weakening medications:
 - Has received treatment with biologics (eg, infliximab, ustekinumab), immunomodulators (eg, methotrexate, 6MP, azathioprine) or cancer chemotherapy within 90 days prior to index date.
 - HIV infection.
- e. Chronic lung disease (ie, Asthma, chronic obstructive pulmonary disease [COPD], interstitial lung disease [ILD]);
- f. Known diagnosis of hypertension;
- g. Cardiovascular disease (CVD), defined as history of any of the following: myocardial infarction, stroke, transient ischemic attack (TIA), heart failure (HF), angina with prescribed nitroglycerin, coronary artery bypass graft (CABG) surgery, percutaneous coronary intervention (PCI), carotid endarterectomy, and aortic bypass;
- h. Type 1 or Type 2 diabetes mellitus;
- i. Chronic kidney disease (CKD) (excluding dialysis or end stage of renal disease);
- i. Sickle cell disease;
- k. Neurodevelopmental disorders or other conditions that confer medical complexity;
- Any cancer diagnoses, other than localized skin cancer (i.e. NMSC) at baseline, within one year prior to index date.

9.3.1.2. Paxlovid Cohort

Paxlovid patients are those who met the inclusion criteria in source cohort and exposed to Paxlovid after EUA approval on December 22, 2021. If a patient had an exposure to paxlovid without COVID PCR or Antigen testing/diagnosis data, this patient can be captured in the Paxlovid cohort.

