There is an urgent and unmet need for antiviral agents that could be used for the treatment of non-hospitalized persons with COVID-19. Paxlovid, a potent and selective inhibitor of the SARS-CoV-2 3CL protease, was developed by Pfizer Inc. as an oral treatment in patients with COVID-19 in outpatient setting. The coronavirus 3CL protease is a virally encoded enzyme that is critical to the SARS-CoV-2 replication cycle, analogous to other obligatory virally encoded proteases (eg, human immunodeficiency virus (HIV) Protease, Hepatitis C virus (HCV) Protease) ⁷ In December 2021, Food and Drug Administration (FDA) has authorized the emergency use of Paxlovid in adult and pediatric patients 12 years of age and older (weighing at least 88 pounds (40 kg)]) with positive results of direct SARS-CoV-2 viral testing, and who are at high risk for progression to severe COVID-19, including hospitalization or death. ⁸

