9.2.1. Study Population and Cohorts

The study population will consist of patients who tested positive or were diagnosed for COVID-19 (ie, positive PCR or antigen results of direct SARS-CoV-2 viral testing or have confirmed COVID-19 diagnosis codes). All Paxlovid users will be included in the study.

Within the study population, three source cohorts of general population with COVID-19 will be formed (Figure 1):

- 1a: Overall COVID-19 patients.
- 1b: Hospitalized patients (ie, hospitalized within 30 days of index date) for COVID-19
- 1c: Non-hospitalized patients (ie, not hospitalized within 30 days of index date) with COVID-19

Within source cohort of 1a, 1b, and 1c, the following trial similar subcohorts, will be formed:

Patients at high risk of progression to severe illness (Figure 1)

- 2a: Subgroup of the general population cohort 1a who meet relevant inclusion/exclusion criteria of the Paxlovid clinical trial (C4671005).
- 2b: Subgroup of the hospitalized patient cohort 1b who meet relevant inclusion/exclusion criteria of the Paxlovid clinical trial (C4671005).
- 2c: Subgroup of the non-hospitalized patient cohort 1c who meet relevant inclusion/exclusion criteria of the Paxlovid clinical trial (C4671005).

Patients at standard risk of progression to severe illness Figure 1)

- 3a: Subgroup of the general population cohort 1a who meet relevant inclusion/exclusion criteria of the Paxlovid clinical trial (C4671002).
- 3b: Subgroup of the hospitalized patient cohort 1b who meet relevant inclusion/exclusion criteria of the Paxlovid clinical trial (C4671002).

[figure not shown]
 3c: Subgroup of the non-hospitalized patient cohort 1c who meet relevant inclusion/exclusion criteria of the Paxlovid clinical trial (C4671002).

A sub-cohort of patients who were exposed to Paxlovid in real world settings will be created.

If a patient had an exposure to paxlovid without COVID PCR/antigen testing/diagnosis data, this patient can be captured in the Paxlovid cohort.

Additional special populations (eg, immunocompromised patients, pediatric population, severe renal impairment, etc.) may be added as a subset.

A validation substudy will be a subpopulation randomly drawn from within the OPTUM EHR database. Figure 1. Flowchart Outlining the Study Cohort and Subcohorts

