9.3.2. Exclusion Criteria

Participants in all cohorts are excluded from the study if the following criterion applies:

1. Missing, unknown, or multiple values for gender.

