9.3.2.1. TSC Standard Risk Cohort and TSC High Risk Cohort

Patients meeting any of the following criteria in the TSC high risk cohort (C4671005) or TSC standard risk cohort (C4671002) will not be included in the study:

1. Females who are pregnant or breastfeeding within 9 months prior to index date.

Any time prior to index date, unless specified otherwise:

- 2. History of hospitalization within 30 days prior to Index date.
- Known medical history of active liver disease (other than nonalcoholic hepatic steatosis), including chronic or active hepatitis B or C infection, primary biliary cirrhosis, or acute liver failure.
- 4. Receiving dialysis or end stage of renal disease.

Additionally, patients meeting any of the following criteria in the TSC standard risk cohort (C4671002) will not be included in the study:

Has at least 1 characteristic or underlying medical condition associated with an increased risk of developing severe illness from COVID-19, including:

- ≥65 years of age at the index date.
- BMI≥30 kg/m².
- "High Risk Cohort Inclusion Criteria 1.c 1.1" (Section 9.3.1.1).

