The Optum COVID-19 EHR dataset elements included patient-level information: demographics, mortality (captured from Social Security Administration Death Master File, electronic medical records and Centers for Medicare and Medicaid Services), as well as clinical interventions, such as medications prescribed and administered, laboratory results, and vital signs and other biometric measures. The data are comprised of multiple tables that can be linked by a common patient identifier (an anonymous, randomized string of characters). The COVID-19 patient data included patients in the EHR database who had documented clinical care from January 2007 through to the most current monthly data release with a documented exposure to, or had been tested for, SARS-CoV-2 (positive or negative result), and/or had a diagnosis of COVID-19, or acute respiratory illness, after February 1, 2020. Thus, not all patients within the Optum® COVID-19 EHR dataset had received a diagnosis of COVID-19. Patients with COVID-19 were identified via a diagnosis code for SARS-CoV-2, a positive test for SARS-CoV-2 active infection (antigen and/or polymerase chain reaction), and/or a positive antibody test. The Optum® COVID-19 EHR dataset included medical records from 2007, allowing for the utilization of patients' medical history in the analysis.

As we are entering new era of COVID 19 toward end of 2022, monthly delivery of OPTUM COVID EHR 19 will be replaced by OPTUM EHR data with longer latency. Additionally, supplemental OPTUM Claims with likely larger size of Paxlovid patients may be used in additional analyses of Paxlovid (if needed) in this study.

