For exploratory analysis, machine learning models (eg, LASSO Cox regression, Random Survival Forest (RSF), and XGBoosting (XGB) models) will be used to identify important predictors associated with progression to COVID-19 severe outcomes/manifestations as well as long COIVD. An ensemble method will be used to rank predictors across models and find the strongest predictors for each outcome. Patient-level prediction for the risk of developing severe outcomes/manifestation and long COVID will be performed using the top ensemble predictors. C-index and dynamic AUCs will be used to evaluate model performance. To assess the feasibility of real-world effectiveness of Paxlovid, we will apply propensity score matching (PSM) method to control confounding and PTDM to handle immortal bias. To better understand the impact of incidental hospitalization on the same date of COVID 19 diagnosis date or Paxlovid prescription date, medical note review of patients with the same date hospitalization will be conducted by OPTUM. The structured data (Hospitalization on the same date = Yes/No) will be provided by OPTUM to enable the assessment of misclassification of the hospitalization.

All data analysis will be executed using statistical software SAS version 9.4 or later.

Detailed methodology for statistical analyses in this study will be documented in a statistical analysis plan (SAP), which will be dated, filed, and maintained. The SAP may modify the plans outlined in the protocol; any major modifications of primary endpoint definitions or their analyses would be reflected in a protocol amendment.

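### The Paxlovid cohort takes users from any care setting, so outcome rates after Paxlovid exposure mix patients already in hospital at prescription with outpatient starters

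*Protocol*

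**What the plan says.** All references are to the protocol.

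- **Who enters.** Section 9.2.1 says "All Paxlovid users will be included in the study". Section 9.3.1.2 adds that "Paxlovid patients are those who met the inclusion criteria in source cohort and exposed to Paxlovid after EUA approval on December 22, 2021". The source population includes inpatients, as cohort "1b: Hospitalized patients (ie, hospitalized within 30 days of index date) for COVID-19".
- **When they enter.** Section 9.2.2.3 sets the Paxlovid index at the first prescription in the study period, with no condition on where it was written.
- **Who is excluded.** The only exclusion for all cohorts (Section 9.3.2) is "Missing, unknown, or multiple values for gender". The criterion "History of hospitalization within 30 days prior to Index date" stands in Section 9.3.2.1, which applies to the two trial-similar cohorts only.
- **Intended setting.** Section 7 describes the product as developed "as an oral treatment in patients with COVID-19 in outpatient setting".
- **Data.** Section 9.6 covers acute inpatient stays as well as outpatient visits, and lists clinical interventions "such as medications prescribed and administered".
- **Outcomes.** Section 9.4 lists hospitalization, all-cause mortality, ICU or mechanical ventilation and in-hospital death as effectiveness outcomes, renal and hepatic impairment as safety outcomes, and time from index to admission. Primary Objective 3 covers incidence after Paxlovid exposure; Primary Objective 5 covers outcomes among treated patients.
- **Nearest safeguards.** Section 9.9 plans a note review to understand the "impact of incidental hospitalization on the same date of COVID 19 diagnosis date or Paxlovid prescription date", and leaves the handling of events before index to the SAP.

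**The concern.** A patient first prescribed Paxlovid during an admission is an eligible user under the text. At that patient's index date the admission has already happened, so time from index to admission is negative or undefined and the hospitalization outcome cannot be read as an event after exposure. Death, ICU care, renal and hepatic events can still occur after index, but from a different starting risk than in someone treated at home.

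A pooled rate then describes neither group. Its value depends on the inpatient share, which may change between annual refreshes. Read as the experience of outpatient users, it could suggest a harm that comes only from the mix. In the feasibility work it could also hide a benefit.

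**Working it through.** **Step 1. Does any provision remove in-hospital starters?**

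- *All-cohort exclusion (9.3.2):* gender data only. No.
- *30-day prior-hospitalization exclusion (9.3.2.1):* trial-similar cohorts only. No.
- *Same-date note review (9.9):* concerns admissions on the diagnosis or prescription date and serves to assess misclassification. It excludes nobody and does not reach a stay that began earlier and is still open.
- *Prevalent-case handling (9.9, left to the SAP):* could stop an earlier admission from counting as a hospitalization event. It would not take the patient out of the death rate or out of rates of new ICU, renal or hepatic events.
- *Cohorts 1b and 1c (9.2.1):* defined by admission within 30 days of index, not by status at prescription. Used as a substitute, 1c would select users on an outcome that may follow treatment.

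**Step 2. How much could it matter?** The protocol states no inpatient share, event rate or sample size, so there is no figure to reproduce. All inputs below are assumptions.

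Let s be the share of users in hospital at prescription, and r_o and r_i the 30-day mortality of outpatient and inpatient starters.

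- Cohort mortality = (1 − s)·r_o + s·r_i
- Inpatient share of deaths = s·r_i / cohort mortality

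With r_o = 0.3% and r_i = 5%:

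| s | Cohort mortality | Ratio to 0.3% | Inpatient share of deaths |
|---|---|---|---|
| 1% | 0.297% + 0.050% = 0.347% | 1.16 | 14% |
| 3% | 0.291% + 0.150% = 0.441% | 1.47 | 34% |
| 5% | 0.285% + 0.250% = 0.535% | 1.78 | 47% |
| 10% | 0.270% + 0.500% = 0.770% | 2.57 | 65% |

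Inpatients supply more than half of deaths when s exceeds 1/(1 + r_i/r_o). Here r_i/r_o = 5/0.3 = 16.7, so the threshold is 1/17.7 = 5.7%.

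**Step 3. Sensitivity to the assumptions.** Over r_o from 0.2% to 1%, r_i from 5% to 15% and s from 1% to 10%:

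- Smallest effect (r_o = 1%, r_i = 5%, s = 1%): 0.99% + 0.05% = 1.04%, a ratio of 1.04, with 5% of deaths from inpatients.
- Largest effect (r_o = 0.2%, r_i = 15%, s = 10%): 0.18% + 1.50% = 1.68%, a ratio of 8.4, with 89% of deaths from inpatients.

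**Step 4. The hospitalization outcome.** Assume 3% of outpatient starters are later admitted.

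- If the open stay is counted as an event, the rate is s + (1 − s)·3%: 3.97%, 7.85% and 12.70% at s = 1%, 5% and 10%.
- If it is not counted but the patient stays in the denominator, the rate is (1 − s)·3%: 2.97%, 2.85% and 2.70%.

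The direction of the error thus depends on a handling rule that the protocol does not give.

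**The case against.** The strongest reply is that a cohort is not an analysis set. This is a descriptive standing cohort, and admitting every user suits the aim of describing treated patients. The protocol leaves refinement of the index date, prevalent cases and subpopulation analyses to a SAP that is not shown, and any of these could carry a setting rule. This stands as far as cohort membership goes, and the fix leaves membership alone. It does not settle the outcome analyses: none of the deferrals mentions setting at prescription, and the one that comes closest, on prevalent cases, does not reach death or new ICU, renal or hepatic events.

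Three further limits stand.

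- Section 9.9 names incidence estimates for the source and trial-similar cohorts only. The Paxlovid rates follow from Primary Objectives 3 and 5.
- The effectiveness work is an exploratory feasibility aim, and Section 9.7 puts post-hoc comparative analyses outside the current scope. Prior hospitalizations and length of stay are listed covariates and could enter the propensity score, though Section 9.9 does not list its variables. Matching would in any case not help the descriptive rates.
- No passage says how many users, if any, start in hospital. Section 9.6 mentions administered drugs without naming Paxlovid, and Section 9.11 stresses prescriptions. Figures 1 and 3 are not shown, so a setting rule drawn there cannot be checked.

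Two stronger readings are tempting. A reader might infer that inpatients would dominate the death and ICU rates. The documents give no figures for this, and under the main assumptions it is true of deaths only above a share of about 5.7%. A reader might also infer that PTDM drops untreated patients with early events while treated patients hospitalized before prescription stay in. Section 9.9 says only that PTDM is meant to handle immortal bias, and not how it treats either group.

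**Conclusion.** The gap is real and should be closed. As written, the protocol lets patients already in hospital at prescription into the outcome rates after Paxlovid exposure and into the PSM/PTDM feasibility work, for a product it describes as an outpatient treatment. Its existing provisions do not clearly remove them.

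The size cannot be known from the protocol. Under assumed 30-day mortality of 0.3% and 5%, inpatient shares of 1% to 10% inflate cohort mortality 1.2 to 2.6 fold; the wider assumed grid gives 1.04 to 8.4 fold. At a very low inpatient share and a modest risk ratio the effect is negligible. The conclusion rests on two premises: that some users start in hospital, and that the SAP and the missing figures contain no setting rule.

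**What to change.** Leave Section 9.3.1.2 as the definition of the descriptive cohort, so that all users stay in the study. In Section 9.9:

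1. Derive a flag for an inpatient stay open at the Paxlovid prescription date. State how a same-date admission is classed; the planned note review can inform this.
2. Run the main Paxlovid outcome analyses and the PSM/PTDM work on users without an open stay.
3. Apply the same rule to comparators at their assigned date.
4. Report in-hospital starters as a separate stratum, with their number and share, so that the effect of mixing can be seen.

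The cost is one derived variable and a slightly smaller main Paxlovid analysis set. The admission and discharge dates it needs should already be held, since length of hospital stay is a listed covariate. The change is analytic only and sets no rule on treatment.

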9.3.2. Exclusion Criteria

Participants in all cohorts are excluded from the study if the following criterion applies:

1. Missing, unknown, or multiple values for gender.

9.3.2.1. TSC Standard Risk Cohort and TSC High Risk Cohort

Patients meeting any of the following criteria in the TSC high risk cohort (C4671005) or TSC standard risk cohort (C4671002) will not be included in the study:

1. Females who are pregnant or breastfeeding within 9 months prior to index date.

Any time prior to index date, unless specified otherwise:

- 2. History of hospitalization within 30 days prior to Index date.
- Known medical history of active liver disease (other than nonalcoholic hepatic steatosis), including chronic or active hepatitis B or C infection, primary biliary cirrhosis, or acute liver failure.
- 4. Receiving dialysis or end stage of renal disease.

Additionally, patients meeting any of the following criteria in the TSC standard risk cohort (C4671002) will not be included in the study:

Has at least 1 characteristic or underlying medical condition associated with an increased risk of developing severe illness from COVID-19, including:

- ≥65 years of age at the index date.
- BMI≥30 kg/m².
- "High Risk Cohort Inclusion Criteria 1.c 1.1" (Section 9.3.1.1).

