9.11. Limitations of the Research Methods

COVID-19 is a new disease with evolving diagnostic mechanisms and care. A COVID-19 diagnosis code was established on 01 April 2020, months after the initial identification of cases and circulation in the US. The validity of the diagnosis codes remains to be determined. The spectrum of clinical manifestations of SARS-CoV-2 is still not fully described. Many infected persons are thought to have mild to unrecognizable symptoms and may therefore not present for care, testing or diagnosis. These infections will likely not be identifiable in the datasets. This may overestimate the incidence of severe disease in relation to overall SARS-CoV-2 infection but should be generalizable in relation to hospitalized patients in relevant analyses.

Similarly, patients with chronic diseases or in inpatient settings, the elderly, or other risk groups may be more likely to be under ongoing care or thought to be at higher risk and therefore may be more likely to seek care or be referred for testing. Differences among at-risk subpopulations may arise from access to care/health care seeking behaviors rather than true differences in risk. Generalizability may be further limited as SARS-CoV-2 testing patterns and treatment are evolving over time.

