Other limitations are similar to those from observational studies in general, including the inability to obtain detailed clinical information on disease severity and activity due to the nature of secondary databases. In addition, EHR data only offer the prescribed drug information which does not indicate that the medication was consumed or that it was taken as prescribed. Misclassification in diagnosis data is unavoidable in real world data (RWD). Some conditions to be used to assess long-term health effects (eg, Dysgeusia, Diarrhea, Myalgia etc.) may not be well captured in the database if the patient is not seen by a health care provider to report these types of events. We use the data from the integrated delivery network (IDN) that manages end-to-end healthcare facilities of one or more healthcare centers in a defined geographical location and aims at providing full spectrum service of inpatient and outpatient for a patient to help reduce the concern of the discontinuity in patient service. We also plan to use the linked data to Claims as sensitivity (or additional) analyses when needed to expand the analyses by adding additional patients or patient records beyond EHR via close or open claims. Lastly, we would also like to note that there is a lack of complete similarity between the Trial Similar Subcohort and the clinical trial patients.

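### Standard-risk status is assigned by the absence of a recorded risk factor, so some patients under 65 with no recorded BMI or smoking status enter that cohort by default and may bias its background rates in an uncertain direction

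*Protocol*

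**What the plan says.** Section 9.3.2.1 (Protocol) builds the standard-risk cohort by removal. After the exclusions shared with the high-risk cohort (pregnancy or breastfeeding, recent hospitalization, active liver disease, dialysis or end-stage renal disease) it states: "Additionally, patients meeting any of the following criteria in the TSC standard risk cohort (C4671002) will not be included in the study". The criterion that follows is "Has at least 1 characteristic or underlying medical condition associated with an increased risk of developing severe illness from COVID-19", spelled out as age 65 or over, BMI of 30 or more, and a cross-reference to the high-risk inclusion items starting at item c. Item c in Section 9.3.1.1 begins "Current smoker (cigarettes smoking at baseline".

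Entry to the high-risk cohort (Section 9.3.1.1) works the other way: at least one listed characteristic must be present.

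Two further rules bear on whether risk factors can be seen:
- The history criterion for all three cohorts in Section 9.3.1.1 is "At least 12 months of ≥1 healthcare activity prior to index date".
- The only exclusion for missing values, in Section 9.3.2, is "Missing, unknown, or multiple values for gender".

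Nothing in Section 9.3 says how a patient with no recorded BMI or smoking status is to be classified.

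**The concern.** Under an exclusion rule, a risk factor that was never recorded looks the same as one that is absent. The default runs one way: missing data can leave a patient in the standard-risk cohort but can never qualify a patient as high risk. (A patient aged 60 to 64 still qualifies as high risk by age, but not because of the missing item.) The history criterion does not ensure that BMI or smoking was captured, and Section 9.5 counts telemedicine visits as healthcare utilization.

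Section 7 says that background rates in patients at high and at standard risk are meant as context for safety events and clinical manifestations in the trials and after marketing. Section 9.9 estimates cumulative incidence and incidence rates in the trial-similar subcohorts. If the standard-risk cohort holds an unknown share of obese patients or smokers, its rate describes a mixture and not the population that its definition names. A reader of the report could not tell how large that share is.

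**Working it through.** **Who defaults in.** The criteria side by side:
- Section 9.3.2.1 removes a patient only when a risk criterion is met.
- Section 9.3.2 removes missing values for gender only.
- Section 9.3.1.1 admits to high risk only on a positive finding.

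The patients affected are those under 65, with BMI or smoking unrecorded, no other recorded risk factor on the standard-risk exclusion list, and none of the shared exclusions. This is a subset of all patients with missing data.

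**Inputs.** The protocol states no missingness share, risk-factor prevalence or event rate, so there is no figure to reproduce. Every value below is an assumption. The base is patients under 65 with no other recorded risk factor, and BMI and smoking are treated as one item that is either recorded or not.
- m = share with the item unrecorded: 0.1 to 0.4
- p = true prevalence of the risk factor: 0.2 to 0.4
- q = its prevalence among the unrecorded: 0.2 to 0.4
- RR = event-rate ratio, truly high risk to truly standard risk: 1.5 to 3
- k = rate multiplier for unrecorded patients; k < 1 if they are healthier or their events are less often captured

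**Step 1: share of the cohort that is truly high risk.**

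C = m·q / [(1−m)(1−p) + m]

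| p | q | m = 0.1 | m = 0.2 | m = 0.4 |
|---|---|---|---|---|
| 0.20 | 0.20 | 0.02/0.82 = 2.4% | 0.04/0.84 = 4.8% | 0.08/0.88 = 9.1% |
| 0.35 | 0.35 | 0.035/0.685 = 5.1% | 0.07/0.72 = 9.7% | 0.14/0.79 = 17.7% |
| 0.40 | 0.20 | 0.02/0.64 = 3.1% | 0.04/0.68 = 5.9% | 0.08/0.76 = 10.5% |
| 0.40 | 0.40 | 0.04/0.64 = 6.3% | 0.08/0.68 = 11.8% | 0.16/0.76 = 21.1% |

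The range is about 2% to 21%.

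**Step 2: effect on the rate.** Relative to the rate in fully recorded, truly standard-risk patients:

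Observed/reference = [(1−m)(1−p) + m·k·(1−q+q·RR)] / [(1−m)(1−p) + m]

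Worked case with m = 0.2, p = q = 0.4, RR = 2, so that 1−q+q·RR = 1.4:
- k = 1: (0.48 + 0.2×1.4)/0.68 = 0.76/0.68 = 1.12
- k = 0.8: (0.48 + 0.224)/0.68 = 0.704/0.68 = 1.04
- k = 0.6: (0.48 + 0.168)/0.68 = 0.648/0.68 = 0.95

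Over p = 0.4, m = 0.1 to 0.4, q = 0.2 to 0.4 and RR = 1.5 to 3:

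| k | Observed/reference |
|---|---|
| 1.0 | 1.02 to 1.42 |
| 0.8 | 0.94 to 1.23 |
| 0.6 | 0.82 to 1.04 |

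**Step 3: where the sign changes.** The rate rises only if k > 1/(1−q+q·RR). The break-even k is 1/1.1 = 0.91 for q = 0.2 and RR = 1.5, and 1/1.8 = 0.56 for q = 0.4 and RR = 3. For an outcome unrelated to BMI or smoking (RR = 1) with k = 1, the ratio is 1.00.

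**Step 4: with the unrecorded patients set apart.** In the fully recorded group m = 0, so C = 0 and the ratio is 1.00 as far as this source of error goes.

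**The case against.** The strongest reply is that handling of missing covariates belongs in the SAP, which is not at hand. Section 9.5 defers code lists and added variables to it, Section 9.2 allows cohorts to be described there, and Section 9.9 lets it modify the protocol's plans. The protocol also never says outright that a missing BMI counts as below 30. This stands in part: an unseen SAP could add a rule. But the cohort definition is fixed in Section 9.3, which does not defer this question and does set one missing-value rule, for gender. As written, the criteria keep these patients.

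A second reply points to safeguards: linkage of inpatient and outpatient records within integrated delivery networks, records back to 2007 (Section 9.6), and linked claims as a possible sensitivity analysis (Section 9.11). The history criterion can also be read as more than one contact in a year. These may reduce missingness, but none tells the analyst what to do when BMI or smoking is still absent. The stated limitation "Misclassification in diagnosis data is unavoidable in real world data (RWD") concerns diagnosis data in general and does not mention this default.

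Three stronger readings are tempting, and the documents do not support them:
- **That standard-risk rates are certainly raised.** Section 9.11 says that "patients with chronic diseases or in inpatient settings, the elderly, or other risk groups may be more likely to be under ongoing care", so sparse records may belong to healthier people. It adds: "Some conditions to be used to assess long-term health effects (eg, Dysgeusia, Diarrhea, Myalgia etc.) may not be well captured in the database" when the patient is not seen. Both push the other way.
- **That every patient with missing data becomes standard risk.** Age, any other recorded risk factor and the shared exclusions still remove patients.
- **That a planned high- versus standard-risk comparison is diluted.** Section 9.9 plans none, and Section 9.7 places comparative analyses outside the present scope.

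**Conclusion.** The concern holds as a matter of cohort definition. Under the criteria as written, patients under 65 with unrecorded BMI or smoking status, no other recorded risk factor and no shared exclusion are classed as standard risk by default, and the missing data can never class them as high risk.

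Contamination of about 2% to 21% rests wholly on assumed missingness of 10% to 40% and assumed prevalence of 20% to 40%. Prevalence may sit toward the lower end, because these patients are already free of recorded hypertension, diabetes and cardiovascular disease.

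The direction of bias is not established. Upward is the likelier direction for severe COVID-19 outcomes if missingness is unrelated to health and care contact. Across the assumptions examined, the observed rate runs from 0.82 to 1.42 times the reference rate. Where k < 1 reflects better health rather than missed events, part of the lower rate is genuine and not error. For outcomes unrelated to BMI or smoking, contamination alone has no effect. An unknown share with an unknown sign is reason enough to make the group visible, since the rate is meant to serve as background for interpreting trial and post-marketing events.

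**What to change.** In Section 9.3.2.1, flag patients who meet no exclusion but have no recorded BMI or no recorded smoking status within a stated look-back before the index date, and place them in a 'risk unclassified' stratum. Report the size of that stratum and its event rates. Give the standard-risk rates twice, without and with the stratum.

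The change needs eligibility wording and two data-presence checks on data already held. The fully recorded cohort will be smaller and tilted toward patients with more care contact, the selection that Section 9.11 warns about; the paired results make that visible. The loss of patients breaks no planned precision target, because Section 9.7 sets no minimum sample size. An added requirement for an in-person visit is not needed, as it would sharpen the selection on care contact.
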